Vascular calcification is a significant problem in dialysis patients that leads to poor outcomes (1-3). Currently there is no therapy that directly addresses this problem. Some of the dialysis solutions (dialysates) currently in use contain citrate, a potent inhibitor of calcium precipitation. In particular, citrate can bind to nascent hydroxyapatite crystals and prevent their propagation (4-5). Blood citrate levels are greater after dialysis with citrate dialysates than with non-citrate dialysates (6), which could slow vascular calcification. However, this has never been investigated. Clinical studies have been limited to the calcification propensity of serum, which decreases with citrate dialysate (7). Administration of citrate to rats with renal failure attenuated vascular calcification (8).

Our research has shown that arterial calcification can be easily detected and reliably measured on routine digital mammograms, with sufficient sensitivity to follow progression (9-13). Mammography is more sensitive in detecting arterial calcification than other imaging and associated with far less radiation and cost. This will allow us to detect differences between citrate and non-citrate dialysates in a safe and convenient way.

4. Study Endpoints

The endpoint will be the difference in the rate of progression of breast arterial calcification (BAC) between dialysis with citrate and non-citrate dialysates.

5. Study Intervention/Investigational Agent

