Dialysate is generated during dialysis from two concentrates (acid concentrate and bicarbonate concentrate) mixed with treated water. When used, citrate is provided in the acid concentrate. For this study, patients will undergo hemodialysis using a citrate acid concentrate (Citrasate; Fresenius Medical Care) or non-citrate acid concentrate (Naturallyte; Fresenius Medical Care), each for one year in a cross-over study. Both acid concentrates are approved for this use by the FDA and will be used according to standard procedures without altered dialysis machine settings. Citrasate is the acid concentrate currently in use at all Emory Dialysis units and the final dialysate is pumped to each patient station from a central location. Therefore, the study intervention will be the use of Naturallyte instead of Citrasate. The Naturallyte will be ordered and stored by dialysis personnel and used by the dialysis technicians or nurses. It will be provided locally at each station as individual containers (the dialyzers are designed to use either centrally or locally supplied dialysate) so there is no risk of non-study patients receiving dialysate from Naturallyte acid concentrate.

6. Procedures Involved

Female hemodialysis patients will undergo screening mammography and those who have BAC will be enrolled. This will be a cross-over study in which half the patients will continue with citrate dialysis and the other half will be switched to non-citrate dialysis. After one year, the patients will be switch to the other dialysis. Dialysis treatments are performed 3 times per week. Mammograms will performed at 6, 12, 18 and 24 months at Emory Healthcare facilities. Patients will have monthly blood draws as part of their routine clinical care and are seen on a weekly basis by the attending nephrologist or nurse practitioner. Data to be collected during the study include:

- measurements of BAC on the mammograms (every 6 months). The mammograms will be interpreted by radiologists.
- plasma citrate, magnesium, and ionized calcium levels immediately before and after dialysis (every 6 months). These will be obtained during routine clinical blood draws and represent an insignificant amount of extra blood.
- routine blood chemistries (monthly as part of clinical protocol)

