will be stored in the Emory Healthcare PACS system, results of research blood assays will be stored in a password-protected file on a HIPAA-compliant server in the Department of Medicine, and results of clinical assays and dialysis parameters will be stored in the Emory Dialysis electronic medical record. Composite data for final analysis will be stored in a password-protected file on a HIPAA-compliant server in the Department of Medicine. Subjects will be assigned unique identifiers, the key to which will be stored as a separate, password-protected file. Access to all data will be limited to the P.I., coinvestigators, and research coordinator. Any transmitted data will not contain any identifiers. Data will be stored until all primary and secondary analyses are completed.

19. Provisions to Monitor the Data to Ensure the Safety of Participants

Patients will be monitored during each dialysis by nurses or technicians, weekly by nurse practitioners, and monthly by attending nephrologists. Clinical data (pre-dialysis labs and anticoagulation) along with intra-dialytic events are already captured per clinical protocol and stored digitally and will be reviewed monthly by the P.I. Oversight of the progress and safety of the trial will be provided by the PI. Adverse events are not anticipated, but any occurring will be documented and reported according to Emory IRB policies and procedures. Cumulative adverse events and study progress summary will be communicated to the IRB at the time of continuing review.

The only potential safety issue relates to the anticoagulant properties of citrate whereby changing to the non-citrate dialysate may increase the risk of clotting of the dialyzer (already a rare occurrence in the outpatient setting). The staff are already trained to recognize the need to increase the heparin dose prior to clotting and this is already captured on the digital dialysis records, which will be reviewed by the study team on a weekly basis for the first month for each subject. If an increased frequency of clotting or need to increase heparin dosing is noted, subsequent subjects will have their heparin dose increased pre-emptively.

Confidentiality will be protected by utilizing a code number as the only identifier for each subject and the master list will be kept under lock and key with access limited to the PI.

The PI will be responsible for reviewing protocol compliance, data collection and verification.

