Cognitively Impaired Adults

- Describe the process to determine whether an individual is capable of consent.
Consultation with the attending nephrologist.

Adults Unable to Consent N/A

Waiver or Alteration of Consent Process (consent will not be obtained, required information will not be disclosed, or the research involves deception) N/A

23. Setting

Describe the sites or locations where your research team will conduct the research.

- Identify where your research team will identify and recruit potential participants.
Outpatient dialysis units.
- Identify where research procedures will be performed. Emory Dialysis Centers and Breast Imaging Centers
- Describe the composition and involvement of any community advisory board. N/A.

24. Resources Available

Subject availability. We will need to recruit 62 subjects to ensure a final sample of 50 allowing for 10% drop-out per year (patients dying, receiving kidney transplants, or transferring to other units). This rate has averaged 9.2% among female patients at Emory Dialysis over the past 9 years. Based on our previous data, 60% are expected to have breast arterial calcification, meaning that 103 will need to be recruited and screened for BAC. There are currently 300 female in-center HD patients within Emory Dialysis and it is estimated that at least 80% or 240 will qualify for screening. Therefore, a recruitment rate no greater than 43% will be required.

Timeline. Recruitment completed: 1 month
Last patient started: 2 months
Last patient: 26 months
Data analysis completed: 27 months

Facilities. Emory Dialysis consists of 4 large outpatient dialysis centers distributed around the Atlanta metropolitan region and is staffed by nephrologists, nurse practitioners, registered nurses, and dialysis technicians. The P.I. will work closely with the managers at each unit and hold educational meetings with staff to ensure that they are adequately informed.

The Emory Breast Imaging Center, consisting of several locations, is staffed by Emory radiologists and performs over 20,000 screening mammograms per year. Mammograms are accessible in the Emory Healthcare PACS system and reports are accessible in the Electronic Medical Record. The Center has procedures in place to contact patients about abnormal findings and discuss/arrange additional followup. The P.I. works closely with

the Medical Director ([name]), who is aware of the protocol and will be the sole radiologist interpreting the mammograms.

25. References

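### The plan describes no masking of whoever measures BAC, its only endpoint, and Sections 6 and 24 disagree on who reads the mammograms

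*Combined protocol and SAP*

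**What the plan says.** Section 4 names one endpoint, the citrate versus non-citrate difference in BAC progression rate. Section 18 obtains each rate by linear regression on three mammograms (months 0, 6, 12 and months 12, 18, 24) and compares the two by a paired test.

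On who reads, two places differ:

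- Section 6, in the bullet on BAC measurements: "The mammograms will be interpreted by radiologists".
- Section 24, Facilities, on the imaging centre's medical director: "who is aware of the protocol and will be the sole radiologist interpreting the mammograms".

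On masking, the plan is silent. The nearest text is in Section 19: "Confidentiality will be protected by utilizing a code number as the only identifier for each subject". That is a confidentiality measure and does not cover dialysate, order or film date. Section 8 keeps the calcification result out of the medical record, which does not mask the person producing it. No reading procedure, batch reading or random film order is described.

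On how allocation could become known:

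- Section 5 says of the non-citrate concentrate, "It will be provided locally at each station as individual containers", while the citrate product is piped from a central supply. The treatment is therefore visible at the dialysis station.
- Section 24 says of the films, "Mammograms are accessible in the Emory Healthcare PACS system and reports are accessible in the Electronic Medical Record". No separate masked set is mentioned.
- Section 24 also describes the principal investigator and the reader as working closely together, and Section 20 gives the investigator unrestricted access to the dialysis records.

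**The concern.** BAC is a length measured from an image by a person, and nothing else in the plan would correct an error in it. If the person measuring knows, or can work out, which dialysate a woman was on at a given film, expectation can move the measurement. The crossover does not protect against this: it removes stable differences between women, not an error that follows treatment. The design also makes one film, month 12, the end of one period and the start of the next, so an error there is counted twice.

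The disagreement on the reader matters for a second reason. If different radiologists measure different films of the same woman, reader differences enter her slopes.

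**Working it through.** **The plan's own figure.** Inputs from Section 18 (Power): SD 11.9 mm/breast/y, taken as the SD of the within-woman rate difference; median rate 20.1 mm/breast/y; 25% change; 80% power; p = 0.05, taken as two-sided.

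- Target difference: 0.25 × 20.1 = 5.025 mm/breast/y.
- Normal approximation: (11.9 × (1.960 + 0.842) / 5.025)² = 44.02, so 45.
- Noncentral t: 46, with power 80.9% at 47 and 83.3% at the planned 50 completers.
- Wilcoxon: 44.02 / 0.955 = 46.1, so 47.

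The stated 47 is reproduced.

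**Weights of the films.** With films at 0, 0.5 and 1 year, the least-squares slope weights are −1, 0, +1, so each slope is last film minus first. Slope 1 minus slope 2 is then

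(y12 − y0) − (y24 − y12) = −y0 + 2·y12 − y24,

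with weights −1, 0, +2, 0, −1 at months 0, 6, 12, 18 and 24. Citrate minus non-citrate has these weights for citrate-first women and the opposite signs for the others.

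**A lean of b mm/breast tied to treatment.** Two patterns:

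- *Month 12 only, in the direction expected for each order.* Citrate-first: 2 × (−b) = −2b. Non-citrate-first: −2 × (+b) = −2b. Average shift 2b.
- *Every on-study citrate film under-read by b.* Citrate-first (months 6 and 12): 2 × (−b) = −2b. Non-citrate-first (months 18 and 24): 1 × (−b) = −b. With equal orders the average shift is 1.5b.

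| Assumed b (mm/breast) | Shift, 1.5b to 2b (mm/breast/y) | Share of 5.025 |
|---|---|---|
| 0.5 | 0.75 to 1.0 | 15% to 20% |
| 1 | 1.5 to 2.0 | 30% to 40% |
| 2 | 3.0 to 4.0 | 60% to 80% |

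A lean equal to the whole target effect would be 5.025 / 2 = 2.5 mm under the first pattern, or 5.025 / 1.5 = 3.35 mm under the second.

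With no true effect, SD 11.9 and n = 50, the two-sided t-test rejects in 9.0% of trials for a shift of 1.0, 14.1% for 1.5, 21.4% for 2.0, 41.6% for 3.0 and 64.4% for 4.0, against a nominal 5%.

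**Reader differences not tied to treatment.**

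- A constant reader offset within a woman cancels: −1 + 2 − 1 = 0.
- A shift c at month 12 common to all women gives +2c in one order and −2c in the other, so the mean is zero when the orders are equal in size. Section 6 plans equal halves: "half the patients will continue with citrate dialysis and the other half will be switched to non-citrate dialysis".
- A change of reader before month 12 that persists gives +c and −c (2c − c, with sign by order). Even with a 28:22 split the mean shift is only 6c/50 = 0.12c.
- What remains is variance. Independent between-reader error of SD s per film adds (1 + 4 + 1)s² = 6s². For an assumed s of 3 mm, the SD is √(11.9² + 54) = 14.0, and power at 50 falls from 83.3% to 70.2%.

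**The case against.** The strongest reply is that silence is not evidence of unmasked reading. A reader might infer that the trial is open label at the imaging centre and that films are measured as they are taken, with dates in view. The documents say neither. Treatment is visible at the dialysis station, which is not where BAC is measured, and the timing of measurement is not given. A reader might also take awareness of the protocol to mean knowledge of each woman's dialysate. In its setting, a description of facilities, it supports knowledge of the study only. Section 18 restricts data access to the investigators and coordinator and keeps the identifier key in a separate file. All this stands: the supportable statement is that no masking is described and nothing rules out that the reader learns allocation.

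It is also tempting to say that a change of reader between visits biases the citrate effect as expectation does. It does not. A change common to all women averages out of the contrast when the orders are equal, and mainly costs precision. If Section 24 governs, it does not arise at all.

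The conflict between the sections may be small. Section 6 may be generic, and both passages may mean clinical interpretation. But then no section clearly says who measures BAC, which still needs a sentence.

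Finally, the size of any lean is assumed. That also stands, and is why a range over two patterns is shown. The film weights follow from Section 18 and are not assumptions.

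**Conclusion.** The point holds as a gap in specification and a cheap improvement. Masking for the only endpoint is not described, the reader is stated inconsistently, and the slope definition doubles the weight of the month-12 film. A treatment-linked lean of 0.5 to 2 mm/breast would move the estimate by 0.75 to 4.0 mm/breast/y, roughly 15% to 80% of the target effect.

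This rests on an assumed lean, on equal orders for the 1.5b average and, for the rejection rates, on SD 11.9 with 50 completers. That SD may already contain some reading error, so the variance example concerns additional error only. The documents do not show that such a lean will occur. The planned sample size is unaffected.

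**What to change.** 1. Reconcile Sections 6 and 24, and name who measures BAC, as distinct from who issues the clinical mammogram report.
2. State in Sections 6 and 18 that one reader measures all five films of each woman as one set after her last visit, with identity, date, dialysate and order removed and the films in random order. The screening read decides eligibility only; the month-0 film is measured again within the set.
3. State that clinical reads for breast findings continue in real time.

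Cost: no extra imaging and no extra reader. The coordinator, or another person without a reading role, needs time to prepare the masked sets. Section 20 limits the coordinator's use of the hospital record to mammogram scheduling, so that wording may need to change. About 50 × 5 = 250 films must be measured in roughly months 24 to 27. Section 24 has the last woman finishing at month 26 and analysis complete at month 27, so the sponsor should confirm this is workable.

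Masking is only partial if the same radiologist also does the real-time clinical reads, having already seen each film with its labels. Removing labels and randomising the order still limits expectation bias.
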